8.8.1.2.3 Vital Signs

Vital signs (blood pressure [systolic and diastolic] and HR) will be recorded as described in the flow chart in a standardized manner, ie, after the subject has rested in the sitting position for 5 minutes.

8.8.1.2.4 Physical Examination

A physical examination will be performed at times as described in the flow chart. Any changes will be recorded.

8.8.1.2.5 Other Safety Assessments

12-Lead ECG

A resting 12-lead ECG will be performed at times presented in the flow chart.

Subjects should rest for at least 5 minutes in the supine position before ECG evaluation.

Parameters to be recorded in the eCRF include: HR, RR, QRS, uncorrected QT, morphology, and rhythm analysis. QTcF will be derived during the statistical analysis. ECGs will be interpreted by the investigator for clinical significance and results will be entered into the eCRF.

8.8.1.3 Flow Chart

Event	Entry Visit	Treatment period ^a			FUV FV + 2 weeks Or EDV + 2 weeks
		D -1 ^c	QEV (q12 weeks)	AV (q48 weeks)	
Study schedule ^b					
Informed consent	X				
Inclusion/ exclusion criteria	X				
Withdrawal criteria		X	X		
Physical examination		X	X	X	X
Pregnancy test ^d	X	X	X	X	X
12-Lead ECG		X	X	X	X
Vital signs ^e		X	X	X	X
TB blood test	X		X		
Clinical laboratory tests ^f		X	X	X	X
IXRS call	X	X	X	X	
Study medication dosing					
Serum CRP		X	X	X	
SJC66		X	X	X	
TJC68		X	X	X	
Physician's global assessment		X	X	X	

Event	Entry Visit	Treatment period ^a			FUV FV + 2 weeks Or EDV + 2 weeks
		D -1 ^c	QEV (q12 weeks)	AV (q48 weeks)	
Study schedule ^b					
Patient's global assessment		X	X	X	
HAQ-D		X	X	X	
FACIT fatigue scale			X	X	
SF-36 questionnaire			X	X	
AE assessment					
Concomitant medications					

- a. During the treatment period, a visit time window of ± 1 week is allowed for each quarterly visit.
- b. QEV=Quarterly Evaluation Visit every 12 weeks; AV=Annual Visit every 48 weeks; FV=Final Visit; EDV=Early Discontinuation Visit; FUV=Follow-Up Visit.
- c. Entry Visit data are those collected at the last visit from the previous core study in which the subject has participated (GLPG0634-CL-203 or GLPG0634-CL-204) for physical examination, 12-lead ECG, vital signs, clinical laboratory tests (including serum CRP and serum pregnancy test), SJC66, TJC68, Physician's Global Assessment, Patient's Global Assessment, HAQ-DI, FACIT fatigue scale, and SF-36 questionnaire, with the exception of demographics, baseline disease characteristics, and medical history.
- d. For female subjects of childbearing potential only. Urine pregnancy test will be performed at Entry Visit and QEV and serum pregnancy test will be performed at AV, Final Visit/EDV and Follow-up Visit. In addition, home urine pregnancy testing will be performed every 4 weeks using home testing kits provided to the subject, as described in Appendix 13.8.
- e. Vital signs are defined as heart rate and blood pressure (systolic and diastolic).
- f. Refer to Section 8.8.1.2.2.

8.8.2 Appropriateness of Measurements

The safety and efficacy assessments are widely used and generally recognized as reliable, accurate, and relevant to the disease condition.

8.9 Statistical Methods

8.9.1 Statistical and Analytical Plans

A detailed statistical analysis plan will be created and finalized prior to database lock.

8.9.1.1 Datasets or Populations Analyzed

All subjects who received at least one dose of study medication in the GLPG0634-CL-205 study will be included in the safety analysis.

All subjects who received at least one dose of study medication in the GLPG0634-CL-205 study will be included in the efficacy analysis.

As it is optional that MTX is restarted for subjects rolling over from the GLPG0634-CL-204 study, the analysis tables may keep subjects with/without MTX background therapy separated as well as pooled.

Other subgroups may be studied separately, when the sample size is considered to be of relevant size.

8.9.1.2 Demographic and Other Baseline Characteristics

Demographic characteristics will be listed. Demographic and baseline clinical characteristics; trial termination reasons; concomitant medications; and drug exposure will be summarized using appropriate descriptive statistics, as applicable.

8.9.1.3 Safety Variables

Clinical safety will be evaluated by assessing treatment-emergent AEs (TEAEs), physical examinations, laboratory assessments, ECG results, and vital signs results. The safety analysis may combine the data of all 3 studies (GLPG0634-CL-203, GLPG0634-CL-204, and GLPG0634-CL-205).

A treatment-emergent analysis of AEs will be done, based on the start date of the AE. TEAE (AE and SAE) preferred terms, intensity, frequency, relationship to study medication, dose reductions, and temporary/permanent treatment stops will all be tabulated. An additional analysis based on patient-years of exposure may be added when deemed useful.

Original results and changes from baseline will be summarized for all laboratory, vital signs, and ECG parameters, intended to detect any changes in safety parameters that could be attributed to GLPG0634 dosing. No imputations will be done for safety data in cases where subjects discontinued the study prematurely.

Further subgroup analyses (e.g., a selection of TEAEs with an onset date during the first weeks or months, or a division according to the mean actual dose) and exploratory analyses may be added when deemed appropriate.

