8.1 Overall Study Design and Plan

This is a multicenter, open-label, long-term follow-up study in subjects with RA. An approximate total of 600 subjects will be enrolled in the study after they have completed one of the previous 2 core studies (GLPG0634-CL-203 or GLPG0634-CL-204). All subjects will start the study at the same dose level (filgotinib 200 mg daily, administered either as 200 mg q.d. or as 100 mg b.i.d., depending on the dosing regimen [frequency of intake of active IMP] that was administered during the preceding core study). The investigator may decide to decrease the daily dose of filgotinib to 100 mg q.d. in case of intolerance or safety reasons. Subjects will return to the 200 mg GLPG0634 daily dose after the reasons for decreasing the dose have resolved, and at the investigator's discretion. Subjects can also continue filgotinib 100 mg q.d. when deemed necessary by the investigator. Subjects coming from the GLPG0634-CL-204 study will be allowed to start MTX treatment, if deemed necessary according to the investigator's clinical judgment.

Subjects have entered the study at Entry Visit on Day -1, which occurred on the same day as the last visit from the previous core study (GLPG0634-CL-203 or GLPG0634-CL-204). Subjects participating in the study have been requested to attend Quarterly Evaluation Visits (QEVs) every 12 weeks. If necessary, unscheduled visits can occur in between the scheduled study visits, for instance, in case the dose of study medication is to be adapted. In case of early withdrawal, an Early Discontinuation Visit (EDV) will be scheduled.

The duration of the participation and treatment for any subject in this study is expected to last for several years (from Entry visit to Follow-up Visit) and will be determined by the sponsor based on the following:

- Open label period (approximately 96 months).
- Marketing Application Approval/Withdrawal in Country of Residence.
- Applicable local reimbursement procedures are in place.

Sites will be notified once these criteria are met.

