Following marketing, local (if applicable) regulatory and/or pertinent local reimbursement approval of the study medication, subjects should return to their next quarterly scheduled study visit as specified in the protocol. This visit will serve as a Final Visit and the subjects will be considered as having completed the treatment part of the study. At the end of the study, subjects will be requested to attend a Follow-up Visit approximately 2 weeks after the Final Visit.

The design of the study is presented in the following table.

Study 203		Roll over to Study 205
Week 1 – 12	Week 13 – 24	
Randomized to placebo	Responders(*) remain on placebo	Half of them are rerandomized to 200 mg q.d. Half of them are rerandomized to 100 mg b.i.d.
	Nonresponders: half of them are rerandomized to 100 mg q.d.	Assigned to 200 mg q.d.
	Nonresponders: half of them are rerandomized to 50 mg b.i.d.	Assigned to 100 mg b.i.d.
Randomized to 50 mg q.d.	Responders remain on 50 mg q.d.	Assigned to 200 mg q.d.
	Nonresponders assigned to 100 mg q.d.	Assigned to 200 mg q.d.
Randomized to 25 mg b.i.d.	Responders remain on 25 mg b.i.d.	Assigned to 100 mg b.i.d.
	Nonresponders assigned to 50 mg b.i.d.	Assigned to 100 mg b.i.d.
Randomized to 100 mg q.d.	Remain on 100 mg q.d.	Assigned to 200 mg q.d.
Randomized to 50 mg b.i.d.	Remain on 50 mg b.i.d.	Assigned to 100 mg b.i.d.
Randomized to 200 mg q.d.	Remain on 200 mg q.d.	Remain on 200 mg q.d.
Randomized to 100 mg b.i.d.	Remain on 100 mg b.i.d.	Remain on 100 mg b.i.d.
Study 204		Roll over to Study 205
Week 1 – 12	Week 13 – 24	
Randomized to placebo q.d.	All assigned to 100 mg q.d.	Assigned to 200 mg q.d.
Randomized to 50 mg q.d.	Responders remain on 50 mg q.d.	Assigned to 200 mg q.d.
	Nonresponders assigned to 100 mg q.d.	Assigned to 200 mg q.d.
Randomized to 100 mg q.d.	Remain on 100 mg q.d.	Assigned to 200 mg q.d.
Randomized to 200 mg q.d.	Remain on 200 mg q.d.	Remain on 200 mg q.d.

(*) responder: having a decrease of at least 20% in tender joint count (TJC)⁶⁸ and swollen joint count (SJC)⁶⁶ versus Baseline.

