8.6.6 Selection and Timing of Dose for Each Subject

The study medication will be administered once daily (in the morning) with a glass of water for q.d. dosing, and twice daily (in the morning and evening) with a glass of water for b.i.d. dosing.

For missed dose(s) of study medication, subjects should be instructed to take the missed dose(s) of study medication as soon as possible during the same day. If the missed dose is not taken on the original day, subjects should be cautioned not to double the next dose with the missed dose of study drug under any circumstances. In those cases, the missed dose should be returned to the study drug bottle.

Dose reduction during the study is allowed in the case of intolerance or safety reasons, where investigators will be allowed to decrease the dose from 200 mg q.d. to 100 mg q.d. or from 100 mg b.i.d. to 100 mg q.d. Subjects will then be allowed to return to the full dose of filgotinib (200 mg q.d. or 100 mg b.i.d. as appropriate) after the reasons for decreasing the dose have resolved, and at the investigator's discretion. Subjects can continue filgotinib 100 mg q.d. when deemed necessary by the investigator.

Further dose reductions during the study are not allowed. Instead, the subject should either temporarily or permanently stop the study drug in accordance with Section 8.4).

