The following decision choice will be used by the investigator to describe the causality assessment between the reported event and the investigational medicinal product.

- Unrelated: No relationship between the AE and the administration of investigational product; related to other etiologies such as concomitant medications or subject's clinical state.
 - Unlikely: Event or laboratory test abnormality, with a time to study medication intake that makes a relationship improbable (but not impossible). Disease or other drugs provide plausible explanations.
 - Possible: Event or laboratory test abnormality, with reasonable time relationship to study medication intake which could also be explained by disease or other drugs. Information on drug withdrawal may be lacking or unclear.
 - Probable: Event or laboratory test abnormality, with reasonable time relationship to study medication intake. Event unlikely to be attributed to disease or other drugs. Response to withdrawal is clinically reasonable and rechallenge not required.
-

- Certain: Event or laboratory test abnormality, with plausible time relationship to study medication intake which cannot be explained by disease or other drugs. Response to withdrawal is plausible (pharmacologically, pathologically). Event definitive pharmacologically or phenomenologically (ie, an objective and specific medical disorder or a recognized pharmacological phenomenon). Rechallenge satisfactory, if necessary.

Action Taken Regarding Investigational Product

The action taken must be described by choosing among:

- Dose not changed: In case no action is taken regarding the study medication.
- Study medication permanently withdrawn: In case a subject is permanently withdrawn from the study.
- Study medication temporarily withdrawn: In case the study medication is temporarily withdrawn.
- Dose reduction: If a subject's daily dose is adjusted from 200 mg to 100 mg (q.d., once daily in the morning).
- Not applicable: Other situations (eg, in case an AE started after the last study medication administration).

Outcome

Each AE must be rated by choosing among:

- Recovered/Resolved.
- Recovered/Resolved with sequelae.
- Not recovered/Not resolved.
- Fatal.
- Recovering/Resolving.
- Unknown.

8.8.1.2.1.2 Recording Adverse Events

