1.2. Study Design

This is a multicenter, open-label, long-term follow-up study in subjects with RA. An approximate total of 600 subjects will be enrolled in the study after they have completed one of the previous 2 core studies: (GLPG0634-CL-203 or GLPG0634-CL-204). All subjects will start the study at the same dose level (filgotinib 200 mg daily, administered either as 200 mg q.d. or as 100 mg b.i.d., depending on the dosing regimen (frequency of intake of active IMP) that was administered during the preceding core study). US males were limited to dosing with filgotinib 100 mg q.d. due to an FDA requirement based on a non-clinical testicular toxicity signal.

The investigator may decide to decrease the daily dose of filgotinib to 100 mg q.d. in case of intolerance or safety reasons. Subjects will return to the 200 mg filgotinib daily dose after the reasons for decreasing the dose have resolved, and at the investigator's discretion. Subjects can also continue on filgotinib 100 mg q.d. when deemed necessary by the investigator. Subjects coming from the GLPG0634-CL-204 study will be allowed to start MTX treatment, if deemed necessary according to the investigator's clinical judgment.

Subjects will enter the study at Entry Visit on Day -1, which will occur on the same day as the last visit from the previous core study (GLPG0634-CL-203 or GLPG0634-CL-204). Subjects

participating in the study will be requested to attend Quarterly Evaluation Visits (QEVs) every 12 weeks. If necessary, unscheduled visits can occur in between the scheduled study visits, for instance, in case the dose of study medication is to be adapted. In case of early withdrawal, an Early Discontinuation Visit (EDV) will be scheduled.

The duration of the participation and treatment for any subject in this study is expected to last for several years (from Entry visit to Follow-up Visit) and will be determined by the sponsor based on the following:

- Open label period (approximately 96 months).
- Marketing Application Approval/Withdrawal in Country of Residence.
- Applicable local reimbursement procedures are in place.

Sites will be notified once these criteria are met.

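### Dividing adverse events by mean actual dose sorts subjects partly by the consequences of those events, so this optional split can show a dose difference when dose has no effect

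*Protocol*

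**What the plan says.** Protocol 8.9.1.3 allows further safety subgroup analyses and gives "or a division according to the mean actual dose" as an example. It sets no averaging window, cut-points or formula. The status is optional: "exploratory analyses may be added when deemed appropriate". The same section says that "The safety analysis may combine the data of all 3 studies", and it lists dose reductions among the TEAE results to be tabulated.

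The dosing rules are in three places.
- Protocol 8.1: "All subjects will start the study at the same dose level (filgotinib 200 mg daily", given once or twice daily.
- Protocol 8.6.6: "Dose reduction during the study is allowed in the case of intolerance or safety reasons". No other ground for reduction is given.
- Protocol 8.8.1.2.1 makes reduction an action recorded against an adverse event: "Dose reduction: If a subject's daily dose is adjusted from 200 mg to 100 mg".

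The roll-over table in Protocol 8.1 shows that many subjects took 50 or 100 mg/day in the core studies before moving to 200 mg/day, for example "Nonresponders assigned to 100 mg q.d". SAP 1.2 adds a rule that the protocol does not contain: "US males were limited to dosing with filgotinib 100 mg q.d. due to an FDA requirement".

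The SAP does not list the mean-dose split. SAP 3.2 groups subjects by core study (with methotrexate, or monotherapy) and places 100 mg q.d. in the same group as both 200 mg/day regimens. SAP 7.7 declares no departure from the protocol's safety analyses.

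**The concern.** A dose split is read as a comparison of exposures. Here the exposure variable is partly an outcome. A subject on 200 mg/day who has a troublesome event may be reduced, and the event and all earlier person-time then move to the low-dose group. The protocol would tabulate dose reduction as a safety result and also use it to form the groups.

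If the core studies are pooled there is a second route. SAP 4.2 and 7.1.5.1 count exposure and TEAEs from the first filgotinib dose, which for most subjects was in a core study. A subject who began on a low core dose and left early keeps a low mean, and one who stayed for years approaches 200 mg. The mean dose then partly measures time on study.

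The primary objective is long-term safety, and the primary endpoint concerns 200 mg q.d. and 100 mg b.i.d., which are the same daily dose. The mean-dose division is the only split by dose level that the protocol names for safety. A reader of such a table could draw a dose conclusion that comes from the method.

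**Working it through.** The plan gives no figure for this split. Its one calculation, the sample size 0.7 × (595 + 280) = 612.5 (stated as 612), reproduces but has no bearing here.

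**1. Extension dosing only.** Mean dose = Σ(dose × time) / Σ(time). Under the protocol everyone starts at 200 mg/day, so a mean below 200 requires a reduction for intolerance or safety. The exceptions are the US-male rule and, depending on the formula, interruptions or missed doses. If each reduction follows a TEAE, 100% of the group below 200 mg has a TEAE by construction.

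**2. Three-study mean.** For 24 core weeks at 50 mg/day and then w weeks at 200 mg/day, the mean is (50 × 24 + 200 × w) / (24 + w):
- w = 12: 3,600 / 36 = 100 mg
- w = 48: 10,800 / 72 = 150 mg
- w = 156: 32,400 / 180 = 180 mg
- w = 417 (about 96 months): 84,600 / 441 = 192 mg

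The extension dose never changes in these four cases. Only the time on study does.

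**3. Event rates from Protocol 6.4.** Rate = −ln(1 − p) / (24/52), assuming a constant hazard:
- Any TEAE: 51.5% (study 203) gives 1.57 per person-year; 41.3% (study 204) gives 1.15.
- Serious TEAE: 2.0% (study 203) gives 0.044; 2.9% (study 204) gives 0.064.

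**4. Simulation with no dose effect, all TEAEs.** About 140 TEAEs per 100 person-years (PY), about eight years of follow-up, and the same risk for every subject. Assumed, because the documents give no figures: 2–5% of TEAEs stop treatment and 1–2% reduce it.
- Extension dose only: any TEAE in 100% below 200 mg against 92–93% at 200 mg. Rates are 152–177 against 137–139 per 100 PY, so the ratio lies between 152/139 = 1.09 and 177/137 = 1.29.
- Three-study mean, lowest against highest stratum: 167–194 against 135–138 per 100 PY, so between 167/138 = 1.21 and 194/135 = 1.44.

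A second set of runs looked at extension dosing only. It assumed that 0.5–5% of TEAEs cause a lasting reduction and that 10% of subjects drop out per year. The ratio was 1.65–1.96 at 1 year, 1.23–1.35 at 3 years and 1.10–1.16 at 8 years. When risk differed between subjects (gamma frailty variance 0.5 or 1), it was 1.65–3.1.

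Subjects held at 100 mg by rule dilute the effect. With 5% of subjects so held, 1% of TEAEs causing reduction and 8 years, the contrast was 97.0% against 92.5% (1.43 against 1.34 per person-year). With no event-driven reductions it vanished (93.2% against 93.1%).

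**5. Events that end treatment.** Protocol 8.4.2 lists events, such as serious infections, for which study drug is stopped permanently. A subject who stops while on 200 mg keeps a mean of 200 mg. A subject in the reduced group must first have stayed on treatment long enough to be reduced.
- Extension dose only: the direction reverses. 8.3% at low dose against 13.0% at 200 mg (8 years, half of serious events ending treatment), and 2.4% against 4.7% (1 year, all ending treatment).
- Three-study mean, no reductions, true rate 5 per 100 PY, half ending treatment, other drop-out 10% per year: 27 (<150 mg), 8.9 (150 to <190) and 4.0 (≥190) per 100 PY at 8 years, and 27, 4.4 and 4.3 at 3 years. The high-mean group looks safer.

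**6. The alternative, dose taken at onset.** With no dose effect and equal risk, the ratio of 100 mg to 200 mg was 0.98–1.01. With frailty variance 0.5 it was 1.5–1.6, and with variance 1 it was 2.0–2.1. Two runs under other settings gave 158/129 = 1.2 and 160/113 = 1.4. The structural bias goes; the higher underlying risk of reduced subjects remains.

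**The case against.** The strongest reply is that nothing planned depends on this. The split is one example in a list of analyses that may be added, the SAP does not take it up, and the analyses are descriptive. That stands and limits the consequence. The text is nevertheless in the current protocol, SAP 7.7 does not withdraw it, and Protocol 8.9.1.5 foresees integrated analyses for registration in which a dose table might be wanted.

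A reader might infer four stronger things, which the documents do not support.
- *That a low mean dose is always caused by events.* US males were held at 100 mg q.d. by rule (SAP 1.2). Core doses were randomised, or reassigned on joint counts. Drop-out for other reasons also lowers a three-study mean. "Largely determined" is as far as the text goes.
- *That the split always shows more harm at lower doses.* Step 5 shows the reverse for treatment-ending events on extension dosing alone.
- *That the false difference in all TEAEs is several-fold at equal risk.* That needs a TEAE rate near 15 per 100 PY with some 40% of events changing treatment. The core incidences imply about 115–157 per 100 PY, and adverse events led to discontinuation in only 3.9% (study 203) and 2.5% (study 204) of filgotinib subjects.
- *That the primary safety results are compromised.* The overall TEAE tables do not use mean dose.

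It is also fair to say that dose at onset is no cure. Step 6 confirms that it still shows a false excess at 100 mg when subjects differ in risk.

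**Conclusion.** The point holds as a caution about an optional analysis. Mean actual dose is a post-baseline variable, largely set by adverse events and, with pooling, by time on study, so the split is biased even when dose does nothing. For all TEAEs it favours 200 mg/day. For treatment-ending events its direction depends on an averaging window that the protocol does not define.

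The size cannot be fixed, because neither document gives the frequency of reductions or the number of US males. For all TEAEs over about eight years, the false ratio is about 1.1–1.4. This rests on the core-study rates, on the assumed 2–5% of TEAEs stopping and 1–2% reducing treatment, and on equal risk. Shorter follow-up or unequal risk makes it larger. For treatment-ending events under pooling, the illustrative contrast in step 5 is wider still. The change is worth making because it is cheap, although no planned table is wrong without it.

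**What to change.** In Protocol 8.9.1.3 replace the mean-dose division with TEAE rates per person-time by the daily dose being taken at onset. Split each subject's events and time into periods at 50, 100 and 200 mg/day, combining once- and twice-daily regimens by total daily dose. Count each event at the dose taken on its onset date, before any reduction made because of it. State how interrupted days are counted. Put the same rule in SAP 7.1.6 for use if any dose-based safety table is produced.

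Show subjects held at 100 mg q.d. by rule separately from those reduced for safety. Label the post-reduction 100 mg row descriptive and confounded, since reduced subjects are likely to be at higher risk and dose at onset does not remove that.

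The cost is a sentence or two and a dose-period dataset built from existing dosing records. The downside is a small, selected 100 mg row.

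Separately, the SAP 1.2 limit for US males and the protocol's statement that all subjects start at 200 mg daily contradict each other and must be reconciled.
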